## PROTOCOL AUTHORISATION

Protocol Title	Antifungal stewardship opportunities with rapid tests for fungal infection in critically ill patients.
Protocol Acronym (if applicable)	A-Stop
Protocol Number	B17/23
Protocol Version Number/Date	v8.0_27/05/2021
Protocol Amendments	v1-v2 key changes 9.2.1 Blood sampleincreased from approximately 12mL to approximately 14mL in adult participants. v2-v3 key changes 8.0 Informed consent -removal of reference to Scottish sites/processes 9.1 Schedule of assessments -timing of standard care blood culture changed to within 24 hours of starting antifungal treatment -additional risk factors added for assessment of probable Candida infection 14.9 Patient confidentiality -an exception to unique trial identifier pseudonymisation is noted as NICTU determining participant mortality via the participant's GP v3-v4 key changes Inclusion criterion changed- Prescribed systemic antifungal therapy, for suspected or confirmed Candida infection, during the preceding 24 hours. Exclusion criterion added- Treatment with antifungal therapy for superficial Candida infection (e.g. thrush) 7.1 - Confirmation of eligibility by a person suitably qualified by education, training or experience. 9.2.1 - Blood sampling: For children, the preferred research sample volume is 4mL, however, this may be either increased or decreased as deemed appropriate by the clinical team up to a maximum of 14mL 9.2.1- Blood sampling: research blood should be obtained as soon as possible within 24 hours of the standard care blood culture. v4-v5 key changes Exclusion criterion removed- Treatment with antifungal therapy for superficial Candida infection (e.g. thrush) 9.1 Glucocorticosteroid treatment paediatric prednisolone equivalent dose added  v6 withdrawn  v5 - v7 key changes 1_Study Summary: Exclusion criteria: added Proven or suspected active infection with COVID-19 Target Sample Size: reduced to 1250

Doc No: TM09-LB01 Protocol Version 8.0 Final\_27.05.2021 Page 2 of 42

Study Duration: extended to 63 months

Co-investigators:

[name] replaced by [name] as Co-investigator.

Trial Statistician: replaced as [name].

6 Study design

6.3 Study Schematic Diagram

Figure 1: Revised study infection numbers inserted

6.4 Study Timeline

Table 1: Updated Study Timeline Gantt Chart

7 Patient eligibility, screening and recruitment

7.1.2 Exclusion criteria:

Proven or suspected active infection with COVID-19

7.4 Recruitment

Adjusted numbers of patients to be recruited from 1750 to 1250 as per study extension. Added that recruitment is estimated at one patient per site per month.

#### 8 Informed consent

Reference made to the Mental Capacity Act 2016 for patients without capacity in Northern Ireland.

- 8.1 & 8.2 Added 'If possible, this Telephone Agreement can be followed up by written consent' to allow the verbal consent.
- 8.5 To clarify what data will be retained in the event of patient withdrawal.
- 9 Schedule of assessments and study procedures
- 9.1 To redefine the timeline for EQ5D5L questionnaire.
- 9.2.1 Blood Sampling

Wording has been added to explain that research blood samples are 'paired' with standard care blood cultures taken and, if these are not taken at the same time as 'paired' blood cultures, then should be obtained as soon as possible within 24 hours of the 'paired' standard care blood culture using the same sampling technique when possible.

9.2.3 To redefine the timeline for EQ5D5L questionnaire.

- 11 Statistical considerations
- 11.1 Sample Size

Sample size figures adjusted from 1750 to 1250. Prevalence of disease reduced from 5% to 4%.

Method for revision of sample size calculation updated

## LIST OF ABBREVIATIONS

Abbreviation /	Full Wording
Acronym	ruii wording
AIK	Akaike's Information Criteria
APACHE	Acute Physiology and Chronic Health Evaluation
BDG	Beta-D-glucan
BHSCT	Belfast Health and Social Care Trust
CI	Chief Investigator
CRF	Case Report Form
CTU	Clinical Trials Unit
DIC	Deviance Information Criteria
EQ-5D-5L	EuroQol-5 Dimension Questionnaire (5 level version)
EU	European Union
FDA	Food and Drug Administration
GCP	Good Clinical Practice
GP	General Practitioner
HRA	Health Research Authority
HRQoL	Health Related Quality of Life
ICH	International Conference on Harmonisation
ICNARC	Intensive Care National Audit & Research Centre
ICU	Intensive Care Unit
ISF	Investigator Site File
ISRCTN	International Standard Randomised Controlled Trial Number
LCM	Latent Class Models
MDT	Multi-disciplinary Team
MHRA	Medicine and Healthcare Products Regulatory Agency
Newcastle MIC	Newcastle In Vitro Diagnostics Co-operative
NHS	National Health Service
NIHR HTA	National Institute for Health Research Health Technology
	Assessment
NICE	National Institute for Health and Care Excellence
NICTU	Northern Ireland Clinical Trials Unit
NPV	Negative Predictive Value
PI	Principal Investigator
PCR	Polymerase Chain Reaction
PELOD-2	Paediatric Logistic Organ Dysfunction (2)
POC	Point of Care
PSSRU	Personal Social Services Research Unit
QALY	Quality Adjusted Life Year
QUB	Queen's University Belfast
RCT	Randomised Controlled Trial
REC	Research Ethics Committee
RMP	Registered Medical Practitioner Receiver Operator Characteristic
SOFA SOP	Standard Operating Procedure
	Standard Operating Procedure
SSC	Surviving Sepsis Campaign Standards for Reporting of Diagnostic Assurage
STARD	Standards for Reporting of Diagnostic Accuracy
TMF	Trial Master File
TMG	Trial Management Group
TSC	Trial Steering Committee
UK	United Kingdom

Doc No: TM09-LB01 Protocol Version 8.0 Final\_27.05.2021 Page 8 of 42

## STUDY SUMMARY

Protocol Title	Antifungal stewardship opportunities with rapid tests for fungal infection in critically ill patients.										
Health condition(s) or problem(s) studied	Rapid test for fungal infection										
Study Design	A multi-centre, prospective, diagnostic test accuracy study.										
	Aim The purpose of this project is to assess the performance of three rapid tests for fungal infection. The accuracy of these tests will be compared and the optimal test (or combination) identified. The emphasis will be on their ability to rule-out infection.										
	Main Objectives: The main objectives of this study are:										
	(i) To assess the diagnostic accuracy of three commercially available rapid tests for Candida infection (beta-D-glucan and two PCR-based tests) in the UK critical care setting.										
	(ii) To develop a test-based protocol, that could be used to guide antifungal drug prescribing in this setting.										
Study Aim and Objectives	Secondary Objectives:										
	The secondary objectives of this study are:										
	(i) To model the clinical effectiveness of implementing the resultant protocol in UK intensive care units (ICUs) as a tool for more appropriately targeting antifungal therapy.										
	(ii) To estimate the proportion of patients currently receiving empirical antifungal therapy in UK ICUs for whom treatment is not clearly indicated.										
	(iii) To model the cost effectiveness of implementing a protocol in UK ICUs, taking account of both beneficial and adverse consequences.										
	(iv) To assess patient and physician risk preferences, for using the tests to discontinue presumptive antifungal therapy.										

Doc No: TM09-LB01 Protocol Version 8.0 Final\_27.05.2021 Page 9 of 42

	(v) To use these data, along with value of information analysis, to estimate the potential utility of, and propose the design for, a future randomised trial.
Primary Outcome	The primary outcome measure is negative predictive value for each index test. Other diagnostic test accuracy measures will also be reported to support this. The analysis for this primary outcome will be based on an international consensus reference standard for proven invasive fungal disease, applied for Candida infection.
	Secondary outcome measures of the study are based on:  (i) Measures of diagnostic test accuracy, for each test alone and in combination, based on an international consensus reference standard for proven invasive fungal disease, applied for Candida infection. These will comprise sensitivity, specificity, positive/negative
	sensitivity, specificity, positive/negative predictive values and positive/negative likelihood ratios.  (ii) Measures of diagnostic test accuracy, for each test alone and in combination, based on an international consensus reference standard for proven and probable invasive fungal disease, applied for Candida infection.
Secondary Outcomes	(iii) Estimated proportion of patients receiving systemic antifungal therapy in this cohort for whom treatment is unnecessary, derived from the reference standards used. Estimated number of days' avoidable antifungal treatment if negative index test results were used to stop treatment.
	(iv) Development of a test-based protocol using the index tests (alone or in combination), as a strategy for early cessation of empirical antifungal treatment, with assessment of its expected cost-effectiveness modelled on test accuracy, disease prevalence and clinical/economic outcomes in this patient group.
	(v) Risk preferences of clinicians and patients supporting an evaluation of barriers to test adoption.

Doc No: TM09-LB01 42 Protocol Version 8.0 Final\_27.05.2021

Inclusion and Exclusion Criteria	
 
Inclusion criteria:         
 
Adults and children >4 weeks old.
 
Admitted to a UK ICU (level 2 or 3).
 
Prescribed systemic antifungal therapy, for suspected or confirmed Candida infection, during the preceding 24 hours.
 
 
 
Exclusion criteria:         
 
More than 24 hours systemic antifungal therapy in the preceding 7-days.
 
Treatment with antifungal therapy for proven or suspected mould infection (e.g. aspergillosis).
 
Neutropenia (absolute neutrophil count <0.5x10^9/L) during preceding 28 days.
 
Acute leukaemia or within 12 months of bonemarrow transplantation.
 
Hospitalised prisoners
 
Previously enrolled in this study.
 
Proven or suspected active infection with COVID-19
 
 
 

Countries of Recruitment	United Kingdom
Study Setting	Adult and paediatric Intensive Care Units (ICU)
Target Sample Size	1250
Study Duration	63 months

Doc No: TM09-LB01 42

#### 3. BACKGROUND AND RATIONALE

## 3.1 Background Information

## 3.1.1 Invasive Candida infection is an uncommon but important disease among patients in UK ICUs

Data from the FIRE Study, which included over 60,000 admissions to 96 UK ICUs, indicate that only 0.6% of patients in UK ICUs are either admitted with invasive fungal infection or develop this during their ICU episode [1]. Around half of these (0.32%) acquired their fungal infection while in the ICU. Candida was the type of fungus implicated in almost all of these cases and bloodstream infection was the most common primary site of infection. ICU remains an important target population, with almost half of candidaemias in UK hospitals arising among ICU patients [2]; invasive candidiasis has been reported to occur up to 10 times more frequently in ICUs than other healthcare settings [3].

Overall ICU and hospital mortality in patients with invasive Candida infection in the FIRE study were 29.9% and 39.6%, respectively – significantly higher than was observed among patients without this infection (16.6% & 24.5%, respectively) [1]. This is, broadly, consistent with candidaemia mortality of 40-50% reported in other datasets [4, 5]. Therefore, while invasive Candida infection is uncommon in the UK ICU setting, its high mortality understandably heightens physician-alertness to the possibility of its occurrence and lowers the threshold for starting antifungal therapy on a presumptive basis. This assertion is supported by the FIRE study data, in which 7% of ICU admissions had treatment started while in the ICU [1]. No intervention has yet been established to adjust this risk-based therapy after it has been started, in the setting of diagnostic uncertainty.

## 3.2 Rationale for the Study

## 3.2.1 A small minority of patients in UK ICUs who are treated with a systemic antifungal drug are found to have a definite fungal infection

The FIRE Study revealed that only 5% of patients who had systemic antifungal treatment started during their ICU episode were subsequently found to meet criteria for proven Candida infection [5]. Even if this is an underestimate, it is clear that the vast majority of patients are overtreated. A recent survey in UK ICUs examined indications for starting antifungal treatment; this highlighted that it is common for treatment to be started on the basis of little, or no, evidence of infection [6]. Candida colonisation is common in ICU patients and, since this is one of the recognised risk factors for development of invasive infection, it drives initiation of empirical treatment [6].

Efforts have been aimed towards the development of risk models to predict the occurrence of infection with a view to avoiding delayed treatment in high risk patients. However, in order to develop a model with sufficient sensitivity the positive predictive values of putative clinical risk models are inevitably low [7, 8].

## 3.2.2 New rapid tests offer an opportunity for timely treatment decisions to avoid unnecessary treatment

Tests recently introduced to market, such as the new PCR-based tests, as well as BDG tests, can be completed within one working day and offer the opportunity to influence prescribing decisions at an early time-point. Prior to commercialisation of these Candida PCR tests, the performance of a variety of in-house assays has been described in small series. Collectively,

Doc No: TM09-LB01 Protocol Version 8.0 Final\_27.05.2021 Page 13 of

in meta-analyses, these have shown promising accuracy and it is assumed that commercial tests of a similar nature will perform similarly [9]. BDG is a biomarker that has demonstrable potential for improving the diagnosis of a number of fungal infections, in various populations. including candidaemia and deep-seated candidiasis [10-13].

The most obvious advantage these new tests bring over current culture-based techniques is their speed. Although blood cultures tend to become positive after 2-3 days at least 5-days must lapse before they can be declared negative. After 5-days of presumptive antifungal treatment, even though the patient may have improved for a variety of reasons, doctors are usually unwilling to stop treatment since it is uncertain whether the patient's response is due to antifungal treatment or other factors. By comparison, a negative result obtained within 24hrs of starting presumptive treatment is much more likely to guide antifungal treatment, before the patient is seen to have improved. Hence tests that bring timely results are better able to influence decision-making and redirect conventional practices. The new tests may also bring improved sensitivity, hence higher negative predictive values, than conventional culture methods.

Diagnostic accuracy data currently available for these tests consists of small studies in heterogeneous patient groups. While their performance has been assessed in meta-analyses, it is impossible to be certain that the findings from assimilating low-to-moderate quality data in this way are correct. The diagnostic test accuracy study we propose here will meet this need and offer a pathway to practice change and better targeted antifungal prescribing.

Doc No: TM09-LB01 Protocol Version 8.0 Final\_27.05.2021 Page 14 of

#### 4. STUDY AIMS AND OBJECTIVES

#### 4.1 Research Hypothesis

The rapid tests under study have high diagnostic accuracy for ruling out Candida infection in critically ill adults and children.

#### 4.2 Study Aim

The purpose of this project is to assess the performance of three rapid tests for fungal infection. The accuracy of these tests will be compared and the optimal test (or combination) identified. The emphasis will be on their ability to rule-out infection so that a test-based protocol for early discontinuation of antifungal therapy can be developed.

This test-based protocol will be modelled for clinical and cost effectiveness, accounting for expected beneficial and adverse outcomes. This modelling, together with a value of information analysis, will inform the design of a future clinical & cost effectiveness RCT.

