#### Assumptions:

- (i) In a survey of clinicians, the "minimum acceptable threshold for sensitivity" of a test that would be used to stop empirical antifungals, 90% emerged as an important sensitivity cut-off to influence practice.
- (ii) Based on the above survey, clinicians were asked to select a minimum threshold of NPV to allow discontinuation of antifungals and a value of greater than 98% would satisfy the test performance requirements of all respondents. As the disease prevalence is anticipated to be low, we have set a more stringent criterion of 99% NPV for the sample size calculation.
- (iii) 4% true disease prevalence
- (iv) 92% true test specificity, and 95% true test sensitivity.
- (v) 5% dropout

Among the 1250 participants at least 1188 will provide evaluable data (95%), of whom 48 are expected to have true infection (4%). With up to 4 false negative results with the best index test (or combination), the 95% CI around a point sensitivity estimate of 91.7% would be 80%-97.7%. This indicates the approximate size of the confidence interval envisaged and reflects a degree of precision that is likely to be acceptable to clinicians if the point sensitivity estimate is above 90%.

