#### 11.2 Statistical Methods

The main analysis will be undertaken to estimate the diagnostic test accuracy of each index test, expressed as sensitivity, specificity, positive/negative predictive values (at specified prevalence) and positive/negative likelihood ratios. They will be calculated with their respective 95% confidence intervals, to express precision of these measures. The PCR-based index tests will produce a categorical result whereas the BDG test will produce a quantitative result. The BDG results will be classified as positive or negative before data analysis begins and the cutoff value used for this will be based on established manufacturer recommendations and expert opinion (currently 80pg/mL).

Analysis of test combinations will also be undertaken as a secondary analysis and will include assessment of these accuracy metrics for all possible permutations of index test results. Taking account of FDA guidance, use of a constructed reference standard will be used for the main analysis because of the difficulties inherent in other approaches when there is no perfect reference test available. The main analysis will, firstly, be undertaken using the international consensus definition of proven fungal disease, as applied for Candida infection, as the reference standard to classify participants. This is acknowledged as an imperfect standard; while its specificity for fungal disease is accepted to be high, its sensitivity is the main source of imperfection. Therefore, it is foreseeable that use of this reference standard alone in the analysis may lead to underestimation of the specificity of the index tests; this may arise if the reference standard fails to detect participants with true disease in instances where the index tests correctly detect this. This concern will be mitigated by also using the forthcoming availability of an internationally-accepted expert consensus standard for probable Candida infection which has been specifically developed for application to ICU patients.

Therefore, as well as being completed using the definition of proven infection, the analysis will also be undertaken using this definition of probable infection; hence, in a secondary analysis,

Doc No: TM09-LB01 Protocol Version 8.0 Final\_27.05.2021 Page 27 of

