## 11.5.1 Comparison of the Diagnostic Accuracy of Index Tests Singly and in Combination

The diagnostic accuracy of the index tests (alone and in combination) will be compared initially using Cochran's Q test at the 5% significance level. If significant, then McNemar's test will be used to explore further which test (or combination) is the most accurate compared to the reference standard. Corresponding 95% confidence intervals for the paired differences will also be generated.

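### Section 11.1 gives the selected best test or combination the precision of one pre-specified test, so its sensitivity will read high near the 90% cut-off if the tests perform similarly

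*Protocol*

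**What the plan says.** Section 4.2 sets out the selection step: "The accuracy of these tests will be compared and the optimal test (or combination) identified". Section 11.2 estimates each index test's accuracy and says of the measures: "They will be calculated with their respective 95% confidence intervals, to express precision of these measures". It adds a secondary analysis of combinations that "will include assessment of these accuracy metrics for all possible permutations of index test results". Section 11.5.1 runs Cochran's Q on the same participants and, if it is significant, "McNemar's test will be used to explore further which test (or combination) is the most accurate compared to the reference standard".

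The assumptions in section 11.1 give the base: "Among the 1250 participants at least 1188 will provide evaluable data (95%), of whom 48 are expected to have true infection (4"%). They continue: "With up to 4 false negative results with the best index test (or combination), the 95% CI around a point sensitivity estimate of 91.7"% would run from 80% to 97.7%. The text adds that this "reflects a degree of precision that is likely to be acceptable to clinicians if the point sensitivity estimate is above 90"%.

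The primary outcome (section 5.1) is NPV for each index test, so all three are reported whichever is preferred.

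**The concern.** Choosing the highest of several noisy estimates tends to choose one whose error was favourable. Reporting that estimate unadjusted, from the same patients, makes it optimistic on average. With about 48 infections, one false negative is worth 2.1 points of sensitivity (1/48), and 90% falls between 43/48 (89.6%) and 44/48 (91.7%). A point-estimate criterion at 90% is therefore easily affected.

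The selected strategy is the one meant to become the test-based protocol, a main objective. Section 11.4.2 treats relative sensitivity and specificity as the most important inputs to the economic model, and section 4.2 uses the modelling to inform a future randomised trial. For a rule-out test, overstated sensitivity means understated false negatives, the group section 11.4.2 describes as at increased risk of adverse outcomes.

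**Working it through.** **Inputs from the protocol (section 11.1).** 1250 participants, 5% dropout, 4% prevalence, true sensitivity 95%, true specificity 92%, criterion of point sensitivity above 90%.

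**Assumptions made here.** True sensitivities other than 95%; latent Gaussian correlation between tests of 0 to 0.8 (section 11.5.3 says the two PCR tests are correlated but gives no value); selection of the highest observed sensitivity.

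**1. The plan's own figures.** 1250 × 0.95 = 1187.5, and × 0.04 = 47.5, so about 48 infections. With 4 false negatives, 44/48 = 91.7%, Clopper-Pearson 80.0% to 97.7%: an exact match. The stated powers also fit one pre-chosen test. For NPV the recomputed power is 90.7% (stated 90%). For point sensitivity above 90% it is 92.4% with the number infected random and 90.9% with exactly 48 (stated 93%).

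**2. One fixed test.** With X ~ Binomial(48, s), the estimate exceeds 90% when X ≥ 44. P(X ≥ 44) is 0.134 at s = 85%, 0.302 at 88% and 0.469 at 90%.

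**3. Best of three independent, equal tests.** P(max ≥ 44) = 1 − (1 − p)³:
- 85%: 1 − 0.866³ = 0.35
- 88%: 1 − 0.698³ = 0.66
- 90%: 1 − 0.531³ = 0.85

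**4. Best of three with correlation (simulation, 48 infections).** Ranges cover correlation 0.8 to 0.

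| True sensitivities | Bias of winner (points) | P(estimate > 90%), winner | One fixed test | Lower limit above truth |
|---|---|---|---|---|
| 85/85/85% | +2.9 to +4.3 | 0.28 to 0.35 | 0.13 | 4.6% to 5.4% |
| 88/88/88% | +2.6 to +3.9 | 0.53 to 0.66 | 0.30 | about 4.2% to 5% |
| 90/90/90% | +2.4 to +3.5 | 0.71 to 0.85 | 0.47 | under 2% |
| 90/80/80% | +0.5 to +1.9 | 0.47 to 0.50 | 0.47 (leader) | 1.6% to 4.2% |
| 95/85/85% | +0.2 to +1.1 | 0.91 to 0.93 | 0.91 (leader) | 0.7% to 2.3% |
| 95/80/80% | 0 to +0.3 | about 0.91 | 0.91 (leader) | 0.1% to 1.1% |

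The nominal lower-limit error is 2.5%. Two-sided coverage of the ordinary exact interval stays at about 94.5% or more throughout.

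**5. Wider selection.** Over 18 strategies (single tests plus OR, AND, majority and mixed rules), the bias is about +0.4 to +3.5 points and coverage about 92% to 99%, depending on the assumed selection rule and correlation.

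**6. NPV.** At 4% prevalence and 92% specificity, NPV = 0.8832 / (0.8832 + 0.04 × (1 − s)). At s = 88% this is 99.46%; at the winner's average reading of 91.85% it is 99.63%. The shift is 0.17 points, and both values are above 99%.

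**7. Effect of a correction.** With equal tests at 85% to 90%, a bootstrap that repeats the selection cuts the bias from between +2.4 and +4.3 points to about +0.8 to +1.5. As a cautious bound, a Bonferroni exact interval for 44/48 is 77.2% to 98.3% over three tests and 73.2% to 99.0% over 18 strategies.

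**The case against.** The strongest objection is that selection rules and internal validation normally sit in the SAP, which is not at hand, and that section 11.1 offers its interval only as an approximate size. This stands in part: a reader might infer that no correction is planned anywhere, but all that can be said is that the protocol states none. It does not dispose of the point, because 11.1 itself names the best test or combination as the subject of a single-test interval.

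Other stronger readings are also unsupported:
- **NPV is overstated.** The primary NPV is reported for every test without selection, and a selected strategy's NPV moves by under 0.2 points. One false negative more or fewer does matter for a lower limit near 99% (99.03% with four, 98.89% with five), but that is a matter of precision, not material NPV bias.
- **The confidence interval under-covers.** Two-sided coverage for the best of three stays close to or above nominal. Only the lower limit errs more often than it should, and mainly at true 85% to 88%.
- **A stated share of chosen combinations would truly fall below 90%.** Any such figure needs a selection rule, and the protocol does not give one.

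The objector can also say that equal tests are a chosen scenario, that combinations are secondary and comparisons exploratory, that section 11.4.1 models every test and combination, and that section 11.4.2 explores uncertainty. All true, and they limit the harm. But exploring uncertainty around an optimistic central value does not remove the optimism, and comparing modelled strategies still favours whichever one happened to read high.

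**Conclusion.** The point holds in a limited form. Followed as written, the protocol selects a strategy and estimates its sensitivity from the same roughly 48 infections, and 11.1 gives the winner the precision of a test fixed in advance.

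If the tests perform similarly (assumed equal true sensitivity of 85% to 90%, latent correlation 0 to 0.8), the overstatement is about 2.5 to 4 points. The chance that an 85% or 88% test appears above 90% roughly doubles. At those values the lower confidence limit is wrong about 4% to 5.4% of the time instead of 2.5%.

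The bias depends on how close the tests are. It is about 1 point or less when a 95% test leads by 10 points or more, and up to about 2 points when the leader is at 90% against 80%. The per-test primary results stand as planned.

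**What to change.** 1. In section 11.1, state that 80% to 97.7% applies to a single pre-specified test and that the interval for a selected strategy will be wider.
2. In sections 11.2 and 11.5.1, fix before analysis the candidate strategies and the rule for choosing among them.
3. Report the selected strategy's sensitivity and specificity both uncorrected and with a bootstrap optimism correction that repeats the whole selection in each resample. Say that this removes most, not all, of the bias.
4. Carry the corrected values and their uncertainty into sections 11.4.1 and 11.4.2.

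If the SAP already does this, only the wording in 11.1 needs changing. No extra patients or data are needed. The cost is a little more analysis work, a slightly lower headline sensitivity and a wider interval.
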